4.0 Drug/Device Information

- Clindamycin 1% topical gel
- Benzoyl Peroxide 5% topical gel
- Clindamycin 1% plus Benzoyl Peroxide 5% topical gel
- Lidocaine 2% with epinephrine

5.0 Selection and Withdrawal of Subjects

Inclusion Criteria:

- Age > 18 years

Exclusion Criteria:

- History of antibiotic use in the last month
- Active acne on the back
- Non-English speakers (the study personnel do not have adequate training to converse with and consent in other languages)

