3.0 Study Design

Twelve healthy volunteers who are over the age of 18 will be consented to participate in our study. Those individuals with active acne or those who received a course of antibiotics in the last month will be excluded. The subject's upper back will be sectioned into quadrants above the scapular spine, which will be each assigned a different topical treatment: clindamycin alone, benzoyl peroxide alone, clindamycin plus benzoyl peroxide, and a control, with no topical application. Each application will be applied twice daily for 3 consecutive days. Randomization will be performed using a random number generator to draw numbers 1-4 in order to designate a topical treatment to each quadrant. Quadrants will be labeled with surgical markers to ensure the correct treatment is applied. Research subject will be trained on application using a mirror with the research staff during recruitment.

A 3-mm dermal punch biopsy specimen will be obtained at each site using a commercially available kit after prepping with isopropyl alcohol and sterile injection of local anesthesia with 2% lidocaine with epinephrine. The biopsy sites will be covered with sterile gauze and allowed to heal without closure. Unfortunately, due to procedural limitations, the dermal layer of the skin cannot be accessed without penetrating the epidermis. Thus even separating the dermis from the epidermis is not helpful because the dermis will have been contaminated from potential pathogens from the epidermis during the biopsy procedure.

A total of four punch biopsies will be obtained from the subject's back; one for each of type of topical treatment and the control. The four punch biopsy specimens will then be cultured for *P. acnes*, with serotyping, and held for 21 days to assess for growth. Assessment of growth will be made the USC Microbiology Lab, who will be blinded to the treatment condition.

Pipettes will be used to inoculate the fluid onto the following media: blood agar, chocolate agar, brucella agar, and brain heart infusion broth. This same culture technique was used by Lee et al, in their published study investigating *P. acnes* levels in the dermis of the skin.⁴ In order to determine hemolytic subtype, the samples will also be tested on Brucella Blood agar, as described by Wright et al.⁶

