9.0 Clinical and Laboratory Evaluations

Medical History Assessment Questions:

1. Are you over the age of 18?
2. Are you pregnant or think you could possibly be pregnant?
3. Have you used antibiotics in the last month?

Back Examination:

1. Inspection of the back of any lesions, rash, acne, or deformities.

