10.0 Criteria for Evaluation and Endpoint Definitions

All eligible subjects who meet inclusion criteria will be included in the analysis.

The primary outcome will be positive growth of *P. acnes* on culture. Secondary outcome will be subtyping based on hemolysis. The USC Microbiology lab assess the samples and will be blinded to treatment condition. They will only receive the participant ID and corresponding treatment number.

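### Screening covers antibiotics but not non-study benzoyl peroxide or similar acne products on the back, so the untreated control may be a treated site and the contrast diluted

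*Combined protocol and SAP*

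**What the plan says.** Exposure to antibacterial agents before the study is addressed in three places. The exclusion list in section 5.0 has "History of antibiotic use in the last month". Section 3.0 says that "those who received a course of antibiotics in the last month will be excluded", which is narrower, because a course is not the same as any use. The screening question in section 9.0 is "Have you used antibiotics in the last month".

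The one other skin-related exclusion in 5.0 is "Active acne on the back", checked by inspecting the back (9.0). It concerns the state of the skin, not the products used on it.

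Section 4.0 lists benzoyl peroxide 5% gel, alone and combined with clindamycin, among the study agents. The comparator in 3.0 is "a control, with no topical application". On treatment, 3.0 says "Each application will be applied twice daily for 3 consecutive days"; subjects apply the gels themselves after training at recruitment.

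The discontinuation reasons in 7.0 are side effects and the subject's wish. The data sheet in 16.0 has no field for other products used on the back.

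**The concern.** The plan accepts that recent antibacterial exposure matters, since it excludes recent antibiotic users. But someone who uses benzoyl peroxide would not naturally report it when asked about antibiotics. If the product keeps the back clear, that person also passes the inspection. The rule can therefore be followed exactly and still admit a subject whose control quadrant has been exposed to a study agent.

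Two things depend on the control being untreated: the treatment contrasts in section 12.0, which use the untreated quadrant as the reference, and the 70% rate behind the sample size, which 6.0 describes as a rate without therapy. A subject whose control site is already negative mostly contributes a negative-negative pair, which carries no information in a McNemar comparison. Randomising quadrants within a subject does not help, because whole-back use reaches every quadrant. With 12 subjects, even one or two such people may matter.

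**Working it through.** **Inputs from the documents (6.0 and 12.0).** Control positivity 70%, treated positivity 5%, 12 subjects, McNemar test, two-sided alpha 0.05, target power 80%. Within-subject correlation is not stated; independence is assumed here.

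**Inputs assumed.** The number of users among the 12 (1, 2 or 3) and the positivity p of a user's control site (5%, 35%, 50% or 60%). The documents give neither. Treated sites stay at 5% throughout.

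**Method.** For a pair with control rate p and treated rate 0.05:

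- P(control positive, treated negative) = p × 0.95
- P(control negative, treated positive) = (1 − p) × 0.05

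With b and c the counts of the two discordant types and m = b + c, the exact test rejects when 2 × P(Binomial(m, ½) ≥ max(b, c)) ≤ 0.05. Six discordant pairs all in one direction are the least that suffice: 2 × (½)^6 = 0.031. Power is the total probability of all rejecting (b, c).

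**The plan's own figure.** At p = 0.70 the discordant probabilities are 0.70 × 0.95 = 0.665 and 0.30 × 0.05 = 0.015. Exact power is 86.1% with 12 subjects and 79.9% with 11, so the stated minimum of 12 reproduces. It is not in dispute.

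**With users.** A user with p = 0.05 has discordant probabilities 0.0475 and 0.0475, so the pair is concordant with probability 1 − 0.095 = 0.905. Each user's own rate is applied to that subject, and 0.70 to the rest:

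| Positivity of users' control sites | 1 user | 2 users | 3 users |
|---|---|---|---|
| 5% | 79% | 68% | 56% |
| 35% | 82% | 77% | 72% |
| 50% | 84% | 81% | 78% |
| 60% | 85% | 84% | 82% |

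In the 5% row, mean control positivity is (0.70 × (12 − k) + 0.05 × k)/12, which is 64.6%, 59.2% and 53.8% for k = 1, 2, 3. Applying that average to all 12 subjects instead gives 77%, 66% and 54%, much the same picture.

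All these figures are for one unadjusted comparison. Section 12.0 plans a GEE logistic model with a 3-df test and adjusted pairwise comparisons, which this calculation does not cover.

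**The case against.** Several parts of the opposing case stand.

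- *Size.* The 5% row gives a background user the rate hoped for after the study treatment, which nothing in the documents supports. With milder effects (50% or 60%) power stays at or near 80%. The whole range must be shown, not its severe end.
- *Antiseptic washes.* A reader might put these on a par with benzoyl peroxide. The documents do not support that: section 1.0 reports 70% growth despite Chloraprep, in the study from which 6.0 takes its 70%. The plan also preps every site with isopropyl alcohol.
- *Silence is not permission.* A reader might infer that volunteers are free to use such products up to biopsy, or that exposure is checked only once. Neither is stated. The control definition, "a control, with no topical application", already implies that nothing goes on that quadrant during the treatment days. Section 9.0 sets no time for its question, and the consent pages are not available, so instructions there cannot be excluded. What remains is that the visible text sets no rule on use before enrolment or on whole-back use, and describes no re-check.
- *Objective 1.* One might say that its control prevalence would be too low. Section 2.0 asks about prevalence after topical treatments and does not name the control.
- *Analysis set.* The sentence "All eligible subjects who meet inclusion criteria will be included in the analysis" might be read as a decision to keep exposed subjects. It is a general statement and does not bar a sensitivity analysis.
- *Safeguards.* Excluding active acne and inspecting the back probably remove many users. They do not remove someone whose acne is controlled by the product.

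**Conclusion.** The gap holds for benzoyl peroxide and other topical antibacterial acne products. The visible text neither asks about, restricts nor records their non-study use on the back, although benzoyl peroxide is itself under test. The consequence is dilution of each treatment-versus-control contrast and some loss of power.

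A reader might infer a bias favouring one active arm. That does not follow, because whole-back use affects all quadrants of the same subject and quadrants are randomised.

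With 1 to 3 users among 12, power for a single comparison lies between 56% and 85%, against 86% with none. Where it falls depends on two assumed quantities, the number of users and the positivity of their control sites, and on independent pairs. One user takes power below 80% only in the 5% case. This is an inexpensive improvement to eligibility and data capture; it does not show that the stated sample size is wrong.

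**What to change.** 1. Reword the 5.0 exclusion and question 3 in 9.0 to cover systemic or topical antibiotics, and benzoyl peroxide or other topical antibacterial acne products used on the back. Reconcile both with the wording in 3.0, which refers to a course of antibiotics. The sponsor should set the look-back window; the documents give no basis for choosing one for the non-antibiotic products.
2. State that no such non-study product is used on the back from enrolment to biopsy.
3. Repeat the question on the day of biopsy and record the answer in a new column on the 16.0 sheet.
4. Add to 12.0 a sensitivity analysis without exposed subjects. Antiseptic washes can be recorded in the same column, without being treated as equivalent to a study treatment.

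The cost is some protocol wording, one repeated question and one column. A few volunteers may be excluded or delayed. The sample size stays at 12.

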8.0 Assessment of Efficacy and Safety

Side effects and toxicities to be monitored:

1. Anaphylactic reaction: symptoms include flushing, itching, swelling, difficulty breathing, and fainting.
2. Nerve Weakness
3. Infection
4. Fever
5. Swelling
6. Abscess formation
7. Dizziness
8. Visual Disturbances
9. Headache
10. Nausea
11. Seizure
12. Diarrhea
13. Abdominal pain
14. Arrhythmia (abnormal heart rhythm)

Because only 2-4 mL of 2% lidocaine with epinephrine will be used there will be no longterm follow-up for these subjects.

The principal investigator is the individual responsible for monitoring and reporting the occurrence of adverse events throughout the study. Subjects will be monitored throughout the study. Subjects will be taken off the study participation if they experience any side effects. USC orthopaedic staff will also monitor for any un-anticipated events. Anticipated adverse events are discussed in the Informed Consent Form for this study.

The research team will follow the IRB Adverse Even Policy on mandatory reporting of Serious Adverse Events (SAEs), and we will also report them immediately both orally and in writing to the IRB Program Director within 24 hours of occurrence or recognition.

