12.0 Statistical Considerations

Statistical Analysis:

Primary outcomes will be treatment comparisons on the percentage of subjects with positive cultures for *P. acnes*. Primary outcomes will be analyzed using generalized estimating equations to account for the within-subject correlated outcomes, as all 4 interventions will be evaluated on each subject. Given the dichotomous outcome (presence/absence of *P. acnes*), the analysis will use a logistic model (binomial random outcome with a logit link function). Three indicator treatment variables will be specified (e.g., clindamycin, benzoyl peroxide, clindamycin plus benzoyl peroxide; with lidocaine as the referent group). A 3df overall test of the treatment indicators will test for any differences in positivity for *P. Acnes* among the treatments; pairwise comparisons among the treatments will adjust for multiple comparisons. A two-tailed statistical test will be performed, testing at an alpha of 0.05. Analyses will also be performed based on hemolytic subtypes.

Power Analysis:

Data from previous studies were used to estimate that 70% of cultures will grow positive for *P. acnes* with no therapy.⁴ For a clinically meaningful response, we would expect only 5% of cultures to grow positive for *P. acnes* following treatment. Thus, using a McNemar test for paired proportion comparison, with an alpha of 0.05 and power of 80%, we would need a minimum of 12 biopsies per treatment group to have adequate power.

Sample Size:

We will recruit a minimum of 12 total subjects to achieve adequate power. Because each patient is receiving 4 biopsies, there will be a total of 48 samples.

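### Every volunteer receives clindamycin, benzoyl peroxide and lidocaine with epinephrine, but nothing in the eligibility criteria or history questions screens for known allergy to them

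*Combined protocol and SAP*

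**What the plan says.** Exposure is the same for everyone. Section 3.0 divides the upper back into four quadrants: clindamycin, benzoyl peroxide, the two combined, and an untreated control. Section 12.0 confirms that "all 4 interventions will be evaluated on each subject". On dosing, Section 3.0 states "Each application will be applied twice daily for 3 consecutive days", and on training, "Research subject will be trained on application using a mirror with the research staff during recruitment". The biopsies follow "sterile injection of local anesthesia with 2% lidocaine with epinephrine", and Section 4.0 lists that anesthetic alongside the three gels.

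Section 8.0 gives 14 side effects to monitor. The first reads: "Anaphylactic reaction: symptoms include flushing, itching, swelling, difficulty breathing, and fainting". On what happens next, it says: "Subjects will be taken off the study participation if they experience any side effects". Section 7.0 has a similar discontinuation rule.

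Section 5.0 has one inclusion criterion (age) and three exclusions: "History of antibiotic use in the last month", active acne on the back, and not speaking English. Section 9.0 has three history questions, on age, on pregnancy, and "Have you used antibiotics in the last month", followed by inspection of the back.

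**The concern.** In a parallel-group trial, an allergic volunteer might escape the relevant drug by allocation. Here nobody does: each subject receives both active drugs on the skin and the anesthetic by injection. The protocol recognises a severe allergic reaction as a possible harm, but provides only for watching for it and withdrawing the subject afterwards. Neither step can prevent a first reaction in someone whose allergy is already known, whereas one question before the first dose could.

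The mirror training suggests, though the text does not say so outright, that subjects apply the gels themselves over the 3 days and may do so with no staff present.

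What is at stake is subject safety. The analysis and the planned sample are not affected.

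**Working it through.** The plan states no figure on this point, so the check is mainly a reading of every screening item against the list of agents.

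**Agents each subject receives** (Sections 3.0, 4.0 and 12.0): clindamycin, benzoyl peroxide, lidocaine, epinephrine.

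**Screening items, and whether each would detect a known allergy to any of these:**

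| Section | Item | Addresses allergy? |
|---|---|---|
| 5.0 | Adult age | No |
| 5.0 | Antibiotic use in the past month | No |
| 5.0 | Active back acne | No |
| 5.0 | Language | No |
| 9.0 | Age question | No |
| 9.0 | Pregnancy question | No |
| 9.0 | Antibiotic question | No |
| 9.0 | Back inspection | No |

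The count is 0 of 4 criteria, 0 of 3 history questions and 0 of 1 examination items.

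Three items come closest, and none closes the gap:

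- The antibiotic items look back one month and concern use. A person who reacted to clindamycin years ago and has avoided it since passes both.
- Section 3.0 calls the subjects healthy volunteers but does not define the term so as to exclude drug allergy. The exclusions it repeats are acne and recent antibiotics.
- The data collection sheet in Section 16.0 has a column for adverse events but none for allergy history.

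**Extent of topical exposure** (Section 3.0):

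- Applications per treated quadrant: 2 per day × 3 days = 6.
- Clindamycin is in 2 quadrants: 2 × 6 = 12 applications per subject.
- Benzoyl peroxide is in 2 quadrants: 2 × 6 = 12 applications per subject.
- All gel applications: 3 treated quadrants × 6 = 18 per subject, before the lidocaine injection.

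**Chance of enrolling at least one subject with a known allergy.** Let p be the proportion of enrolled volunteers who know of an allergy to any of the four agents. The documents do not give p, so the values below are assumptions. For 12 independent subjects the chance is 1 − (1 − p)^12:

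| Assumed p | Calculation | Chance of at least one in 12 |
|---|---|---|
| 0.5% | 1 − 0.995^12 | 5.8% |
| 1% | 1 − 0.99^12 | 11.4% |
| 2% | 1 − 0.98^12 | 21.5% |

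These are chances of enrolling such a person. They are not chances of a reaction, still less of anaphylaxis.

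**The case against.** The strongest counter-argument is the consent form. Section 8.0 says that anticipated adverse events are discussed there, so volunteers should learn of the risk before exposure, and people who know of an allergy are the ones best placed to decline. That probably lowers the practical risk, and it makes the assumed values of p, which ignore self-exclusion, more likely too high than too low. But the form is not in the review copy, so it cannot be seen whether it names each agent or asks about allergy. Even a clear warning leaves detection to the volunteer and does not oblige the investigator to exclude anyone.

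A second argument is that the toxicity list is not ranked and does not tie anaphylaxis to the gels. The only agent named in Section 8.0 is lidocaine with epinephrine, which is given at the biopsy, and Section 11.0 reserves the biopsies for trained surgeons. This is fair: nothing should be read into anaphylaxis coming first, and supervision at the injection is a real safeguard. A surgeon may well ask about allergies at that point. The protocol does not require it, however, and by then the 3 days of gel treatment are over.

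Third, the application counts and probabilities do not establish the gap, which would be the same at one application. That is also correct. They describe its extent; the finding rests on the missing criterion and question.

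**Conclusion.** The concern holds. Applied exactly as written, the criteria admit a volunteer with a known allergy to clindamycin, benzoyl peroxide, lidocaine or epinephrine, and the within-subject design guarantees exposure to all four. Sections 5.0 and 9.0 read as complete lists, so this does not look like text lost from the review copy. The conclusion needs no assumption about how common such allergies are; only the 5.8% to 21.5% range does. The sponsor should correct this for subject safety. It has no bearing on the validity of the comparison or on power.

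**What to change.** Make two additions:

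1. In Section 5.0, a further exclusion criterion: known hypersensitivity to clindamycin, benzoyl peroxide, lidocaine or epinephrine.
2. In Section 9.0, a fourth history question: *Have you ever had an allergic reaction to clindamycin, benzoyl peroxide, lidocaine or epinephrine?*

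Both are needed. The question finds the allergy and the criterion makes the answer binding. The pregnancy question shows what happens otherwise: it is asked in Section 9.0 with no corresponding rule in Section 5.0.

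The cost is one line and one question. A few volunteers may be turned away and replaced. There is no added test or visit, and the 12 subjects and 48 samples stand.

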6.0 Sample Size

We will recruit participants until there are 12 total subjects.

Power Analysis:

Data from previous studies were used to estimate that 70% of cultures will grow positive for *P. acnes* with no therapy.⁴ For a clinically meaningful response, we would expect only 5% of cultures to grow positive for *P. acnes* following treatment. Thus, for an alpha of 0.05 and power of 80%, we would need a minimum of 12 biopsies per treatment group to have adequate power, based on a McNemar test for paired proportion comparison.

Sample Size:

We will recruit a minimum of 12 total subjects to achieve adequate power. Because each patient is receiving 4 biopsies, there will be a total of 48 samples.

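### The 80% power behind n = 12 belongs to one unadjusted McNemar comparison, not to the multiplicity-adjusted pairwise comparisons planned in Section 12.0

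*Combined protocol and SAP*

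**What the plan says.** Section 6.0 assumes that 70% of cultures grow without therapy and 5% after treatment. It concludes that "for an alpha of 0.05 and power of 80%, we would need a minimum of 12 biopsies per treatment group to have adequate power", using McNemar's test for paired proportions. Section 12.0 repeats the statement, "using a McNemar test for paired proportion comparison, with an alpha of 0.05 and power of 80" per cent. Both sections then say that 12 subjects give adequate power, and neither limits this to a single comparison.

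The analysis text in Section 12.0 is wider. "Primary outcomes will be treatment comparisons on the percentage of subjects with positive cultures" for the organism, under four conditions applied to every subject. A GEE logistic model is planned. "A 3df overall test of the treatment indicators will test for any differences in positivity", and "pairwise comparisons among the treatments will adjust for multiple comparisons". The level is given once: "A two-tailed statistical test will be performed, testing at an alpha of 0.05".

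The plan does not state how many pairs form the family, which adjustment is used, which version of McNemar's test was used for sizing, or what within-subject correlation was assumed. It gives no power for the adjusted comparisons.

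**The concern.** The sizing spends the whole 0.05 on one paired comparison. The analysis divides or steps that 0.05 across at least three comparisons (each active treatment against control) and up to six (all pairs of four conditions). The overall test can show that the conditions differ somewhere. A statement that a particular treatment lowers positivity rests on an adjusted pairwise test, and the plan gives no power for that test.

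A reader of Sections 6.0 and 12.0 could reasonably take 80% as the power of those tests. If the true power is lower, a non-significant contrast is more likely than the reader expects, even when the assumed 65-point difference is real, and it may be over-read as no effect.

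**Working it through.** **Inputs from Sections 6.0 and 12.0:** control 0.70; treated 0.05; two-sided alpha 0.05; power 80%; 12 subjects, each with all four conditions, so 12 pairs per contrast.

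**Assumptions, because the plan is silent:** the family is three treatment-versus-control pairs or all six pairs. The probability p11 that both sites are positive can run from 0 to 0.05; independence gives 0.70 × 0.05 = 0.035. Then p10 = 0.70 − p11 and p01 = 0.05 − p11, and the discordance p10 + p01 is 0.75, 0.68 or 0.65 at p11 = 0, 0.035 or 0.05.

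**Step 1: reproduce 12.** Power is the sum of the multinomial probabilities of all discordant counts (b, c) whose McNemar p-value is at or below alpha.
- Exact test, independence, alpha 0.05: 79.9% at n = 11 and 86.1% at n = 12. The minimum is 12.
- Continuity-corrected test, independence: also 12, with 86.1%.
- Normal approximation, n = [1.960 × √0.75 + 0.842 × √(0.75 − 0.65²)]² / 0.65² = 11.24, rounded up to 12, at the least favourable discordance.

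So 12 is correct for one comparison at an undivided 0.05.

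**Step 2: what adjustment does.** With exact McNemar and every discordant pair in the same direction, the smallest p-value is 2 × 0.5^m for m pairs: 0.03125 at m = 6, 0.0156 at m = 7, 0.0078 at m = 8. The fewest discordant pairs that can give significance are therefore 6 at 0.05, 7 at 0.05/3 = 0.0167 and 8 at 0.05/6 = 0.0083.

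**Step 3: power at n = 12 by Bonferroni, one treatment-versus-control contrast.** Independence first; range over all compatible discordance in brackets.

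| McNemar version | 0.05 | 0.05/3 | 0.05/6 |
|---|---|---|---|
| Exact | 86% (77–92) | 71% (56–79) | 55% (45–58) |
| Continuity-corrected | 86% (77–92) | 56% (50–58) | 35% (33–35) |
| Mid-p | 93% (85–97) | 82% (67–92) | 71% (56–79) |
| Uncorrected | 95% (86–99) | 82% (67–92) | 71% (56–79) |

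The lowest bracket ends in the 0.05/3 column, and in most of the rest, need p11 = 0, meaning no subject positive at both sites. Nothing in the plan supports that extreme.

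Under independence and without adjustment, mid-p and uncorrected McNemar reach 80% at n = 10 and n = 8. They can keep 80% over three pairs, but they do not explain a stated minimum of 12.

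**Step 4: milder adjustments, by simulation.** Exact McNemar, independence, three treatment-versus-control pairs, all active treatments at 5%, power for a given contrast:
- Bonferroni 71%
- Holm 78% (65–83% over the compatible discordance)
- Hochberg 81%
- Benjamini–Hochberg about 85%, which controls the false discovery rate and not the familywise error

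Holm's gain depends on the other treatments also working. If the other two stay at 70%, Holm gives 71%, the same as Bonferroni.

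**The case against.** The plan names its test, alpha and rates, and never says in terms that the adjusted comparisons have 80% power. The second objective in Section 2.0 asks whether treatment type matters, and the 3-df test answers that at an undivided 0.05. Sizing on one key contrast and adjusting the follow-up comparisons is common in a small volunteer study. All of this is fair, and it is why n = 12 is not an error. It does not remove the gap, because Section 12.0 words the primary outcomes as treatment comparisons, and both sections call 12 subjects adequate without saying for which test.

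A reader might infer that adjusted power must fall below 80% whenever the sizing is read in a way that gives 12. The documents do not support that. No adjustment method is named, and under the exact-test reading that gives 12, Hochberg over three pairs keeps 81% while Holm misses by only about 2 points. Quoting only the Bonferroni figures would overstate the deficit.

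A further objection stands in part: McNemar figures are a stand-in for GEE logit contrasts. They show how the stated basis for 12 behaves once alpha is shared, and are only approximate for the planned model.

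**Conclusion.** The concern holds in a limited form. The 80% is the power of one unadjusted paired comparison and should not be read as the power of the adjusted pairwise tests. The size of the gap depends on open choices. With exact McNemar, independence and all active treatments at 5%, power is about 71% to 81% over three pairs (Bonferroni to Hochberg, familywise methods only), and about 55% for six-pair Bonferroni, the low-end case. With six-pair Bonferroni, every McNemar version stays below 80% at every compatible discordance (33–79%). With three pairs, mid-p or uncorrected McNemar under independence keeps 80% (82%).

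In practical terms, at 71% power a true 70% versus 5% difference would be missed about 29% of the time (100 − 71), against the 20% a reader would expect.

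Two stronger conclusions do not follow. The number 12 is not miscalculated. Nothing here bears on the power of the 3-df overall test, which was not computed. All figures apply to treatment-versus-control contrasts at the assumed effect; the sizing does not address differences between active treatments.

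**What to change.** In Sections 6.0 and 12.0:

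1. State that the 80% applies to one paired comparison of 70% against 5% at an unadjusted two-sided 0.05, and name the McNemar version and the discordance assumed.
2. Before the analysis, name the comparison family (three treatment-versus-control pairs, or all six) and the adjustment method.
3. Restate the power at n = 12 for that choice with its assumptions. For example, with exact McNemar under independence and all active treatments at 5%: about 71% (Bonferroni) to 78% (Holm) for three treatment-versus-control pairs, and about 55% for six-pair Bonferroni, labelled as the low-end case. If a milder method such as Hochberg is chosen, give its figure.
4. Add that McNemar figures only approximate the planned GEE contrasts, and quote no power for the 3-df test from them.

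The cost is wording and an early commitment to a family and method. The sample size, the four conditions and the planned tests stay as they are. The downside is that the stated pairwise power may become less favourable.
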